### **5.2.1 Medical History**

1. Date of visit, subject enrollment number, and subject initials will be recorded at each follow-up visit.
2. Subject eligibility will be verified based on inclusion and exclusion criteria. Adherence to criteria will be noted.

### **5.2.2 Physical Examination**

- Digital assessment of the great toe/planimetry
- Lower extremity focused physical examination for visits at weeks 10, 20, 30, 40. A complete history and physical examination at week 50.

- Vital signs
- Clinical assessment of the toenails

### **5.2.3 Procedures**

- KOH wet mount and fungal culture at final office visit
- Additional safety laboratory studies will be ordered as needed
- Debridement of target toenail
- Debridement of other toenails as needed

### **5.2.4 Adverse Events**

- Each follow-up visit will include careful monitoring for adverse events

## **5.3 Administration of Efinaconazole Methods**

All subjects will be self-administering the medication. All related questions will be answered and concerns addressed.

### **5.3.1 Storage and Handling of Efinaconazole**

Efinaconazole will be stored by the subjects themselves, without requirement of freezing or refrigeration

### **5.3.2 Subject Education**

Subjects will be informed of all beneficial and adverse effects of efinaconazole during the written and oral consent process (refer to sections 3.1 and 4)

### **5.3.3 Subject Compensation**

Subjects will be compensated a stipend for each attended office visit following screening. The amount of compensation will be of reasonable amount, and not excessively large as to inappropriately motivate subjects.

## **6 SUBJECT COMPLETION OR DISCONTINUATION**

### ***6.1 Subject Completion***

The subject will be considered to have completed the study after completed the week 50 follow-up evaluation.

### ***6.2 Subject Discontinuation***

The subject will be discontinued from the study if the subject withdraws, is withdrawn due to an adverse event, or is no longer able to be located. Any reason for discontinuation must be documented along with information about the health of the subject at the time of withdrawal. All attempts to contact subject must be documented. After 3 documented attempts of contact, the subject will be considered discontinued.

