## **2.4 Efficacy Endpoints**

Mycological cure will be defined as negative KOH examination and negative fungal culture of the target toenail sample.

Clinical cure will be defined as 0% clinical involvement of the target toenail. Almost clinical cure will be defined as  $\leq 10\%$  clinical involvement of the target toenail.

Complete cure will be defined as 0% clinical involvement and mycological cure. Treatment success will be defined as  $\leq 10\%$  clinical involvement of the target toenail and mycological cure.

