### **2.4.1 Primary Endpoints**

1. The primary efficacy end point will be the proportion of subjects achieving complete cure at week 50.

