### ***6.3 Early Termination Appointment***

If the subject elects to discontinue the study prior to completion, the subject will be asked to attend an early termination appointment. This early termination appointment will replace the final office visit. It will include the procedures of a follow-up office visit, with the addition of a complete history and physical. Subjects will be provided increased, but not excessive, financial compensation as motivation for attending this appointment.

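### Section 6.2 does not separate stopping efinaconazole from leaving follow-up, so week-50 outcomes are not sought from discontinued subjects who would still attend

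*Combined protocol and SAP*

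**What the plan says.** Section 6.2 (Subject Discontinuation) states: "The subject will be discontinued from the study if the subject withdraws, is withdrawn due to an adverse event". The same sentence covers subjects who cannot be located, and the section adds: "After 3 documented attempts of contact, the subject will be considered discontinued". No time window is attached to the attempts, and no later attempt is mentioned.

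Section 6.3 (Early Termination Appointment) invites a subject who chooses to leave early to one last visit, for increased compensation, and says: "This early termination appointment will replace the final office visit". That visit consists of the follow-up visit procedures plus a complete history and physical.

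Section 2.4.1 (Primary Endpoints) sets the primary endpoint as "the proportion of subjects achieving complete cure at week 50". Section 2.4 (Efficacy Endpoints) defines it: "Complete cure will be defined as 0% clinical involvement and mycological cure". Section 5.2.3 (Procedures) places post-baseline mycology at one time only: "KOH wet mount and fungal culture at final office visit".

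Three other sections bear on the point:
- Section 7.2 (Adverse Events) continues follow-up of an adverse event until it resolves.
- Section 7.1 (Safety Evaluation) defines the intention-to-treat population as subjects with at least one dose and at least one post-baseline assessment. Section 2.2 (Treatment Groups) continues enrolment until there are 48 of them.
- Section 10.5 (Data Handling) requires missing data to be noted with a reason, and says nothing about how they count in the analysis.

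**The concern.** Stopping a medication and leaving a study are different events. A subject withdrawn at, say, week 12 because of a skin reaction may be willing to come back at week 50 for planimetry, KOH and culture. Under 6.2 that subject has left the study, and no section puts the subject back on the visit schedule.

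Complete cure needs a mycology result, and mycology is scheduled once. An outcome not collected at week 50 cannot be recovered at analysis. The gap would also be related to tolerability, which is one of the things the study sets out to describe. With no control arm, no comparison within the study would show whether those who left differed from those who stayed.

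**Working it through.** **1. Is a week-50 outcome sought after discontinuation?** Reading the sections together:
- 6.2: withdrawal for an adverse event means discontinued from the study.
- 6.1: completion means having had the week-50 evaluation.
- 5.2: visits fall at weeks 10, 20, 30, 40 and 50, with no provision for discontinued subjects.
- 6.3: the early visit takes the place of the final one. It reads the nail before week 50. Whether it includes mycology is unclear: it follows the follow-up procedures, and 5.2.3 ties KOH and culture to the final visit. It is offered to subjects who choose to leave, so a subject withdrawn for an adverse event is not clearly offered it.
- 7.2: continued follow-up concerns the adverse event, not efficacy at week 50.

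No section seeks the week-50 outcome once a subject is discontinued.

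**2. The plan's own precision figure.** Section 4 (Subject Selection) gives 0.281 for a 55% mycologic cure rate with 48 subjects. The full width of a Wald interval is 2 × 1.96 × √(p(1−p)/n). With p = 0.55 and n = 48 this is 2 × 1.96 × √(0.2475/48) = 0.281, so the figure is reproduced. It assumes that all 48 subjects contribute an outcome.

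**3. How many subjects are affected?** Section 1.4 cites adverse-event discontinuation on efinaconazole of 3.2% and 1.9% in two phase III studies. Carried over to this study (an assumption): 48 × 0.019 = 0.91 and 48 × 0.032 = 1.54, so about 1 to 2 subjects.

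**4. What does that do to the result?** With m outcomes missing, the span between counting all as failures and all as cures is m/48. The Wald width is recomputed at 55% with n = 48 − m.

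| Missing m | n | Wald width | m/48 (percentage points) | Basis for m |
|---|---|---|---|---|
| 0 | 48 | 0.281 | 0 | plan's figure |
| 1 | 47 | 0.284 | 2.1 | cited adverse-event rates |
| 2 | 46 | 0.288 | 4.2 | cited adverse-event rates |
| 5 | 43 | 0.297 | 10.4 | assumed 10% total loss |
| 10 | 38 | 0.316 | 20.8 | assumed 20% total loss |

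The last two rows show sensitivity only. The documents give no total loss rate, and much of any total loss could not be recovered by a change of wording.

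**5. Which direction?** Suppose 12 cures are observed (an assumption). With 1 or 2 outcomes missing, an observed-case analysis gives 12/47 = 25.5% or 12/46 = 26.1%. Counting missing as not cured gives 12/48 = 25.0%. The two rules differ by 0.5 to 1.1 points, and the plan does not say which applies.

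**The case against.** The strongest reply is that 6.2 is loosely worded rather than wrong. It says that a subject withdrawn for an adverse event is discontinued; it does not say that anyone who stops applying the solution must be withdrawn. Section 6.1 ties completion to the week-50 evaluation, not to continued use. This stands in part: a reader might infer that 6.2 removes every subject who stops treatment, and the text does not go that far. It does give no route by which a subject withdrawn for an adverse event is seen at week 50.

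Four further inferences are tempting and are not supported:
- *Safety observation ends at withdrawal.* Section 7.2 keeps an ongoing adverse event under follow-up until it resolves. Only observation for new events after withdrawal is affected.
- *The cure rate will be biased upward.* That needs an observed-case analysis, which the plan does not specify. If missing counted as not cured, there would be no upward lean.
- *A subject lost after missing the week-10 visit becomes a gap among the 48.* Without a post-baseline assessment that subject is outside the intention-to-treat definition in 7.1 and is replaced under 2.2. The gaps among the 48 come from later losses.
- *Every early loss is due to this rule.* Subjects who refuse further visits or cannot be found are largely beyond its reach. For lost contact the point is narrower: the three attempts have no time window, and none is made at week 50.

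It is also fair that this is an uncontrolled pilot and that 6.3 already pays more to obtain a last assessment. Both points limit the weight of the concern without closing the gap.

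**Conclusion.** The point holds as a modest data-collection gap. As written, week-50 outcomes are not sought from discontinued subjects who would still attend, because one status covers both stopping treatment and leaving follow-up. The case is clearest for adverse-event withdrawals: about 1 to 2 of 48 subjects, or 2 to 4 percentage points between the extreme ways of counting them, set against a planned interval width of 28.1 points (a width stated for mycologic cure, not for the primary endpoint). This rests on the phase III rates cited in 1.4 applying to this diabetic cohort. The effect of all early losses cannot be sized from the documents, and the direction of bias is open until the plan says how a missing week-50 outcome counts.

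**What to change.** In 6.2 and 6.3:
- Define two separate statuses: stopped study treatment, and withdrew consent for follow-up.
- Keep a subject who has stopped treatment but still consents on the visit schedule, including week-50 planimetry, KOH and culture.
- Let the early termination visit replace week 50 only for a subject who declines further visits.
- For a subject who could not be reached, make one further contact attempt at week 50.

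This changes what is collected. It does not supply the missing-outcome rule, which the analysis plan has to state separately. The sample size and the clinical rules for stopping treatment stay as they are.

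The cost is a wording change plus a few extra visits, with the per-visit stipend of 5.3.3, for subjects who would otherwise have left. Some week-50 results will come from subjects off treatment, and the report must identify them.

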### ***6.3 Early Termination Appointment***

If the subject elects to discontinue the study prior to completion, the subject will be asked to attend an early termination appointment. This early termination appointment will replace the final office visit. It will include the procedures of a follow-up office visit, with the addition of a complete history and physical. Subjects will be provided increased, but not excessive, financial compensation as motivation for attending this appointment.

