## **5.2 Follow-up Visits**

Subjects will be assessed at the screening, at baseline, and at every 10 weeks until week 50 (at weeks 10, 20, 30, 40, and 50). The final assessment (week 50) will include a complete history and physical examination, replacing the lower extremity focused physical examination.

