## **7.1 Safety Evaluation**

Safety will be assessed by recording the nature, intensity, and duration of treatment related adverse events. Safety analyses will be performed on both an intention-to-treat and per-protocol analysis basis. The intention-to-treat population will include each patient receiving at least one dose of the medication, with at least one post-baseline assessment.

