## **7.2 Adverse Events**

An adverse event may be any unintended clinical, radiographic, or laboratory result associated with the use of treatment modality. An adverse event does not necessarily have causal relationship with the treatment intervention.

Information collected during subject screening serves to determine if an adverse event started before or during the course of study and to monitor its progression throughout the course of the study. Follow-up evaluation and treatment will continue until the adverse event has resolved.

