### **10.5 Data Handling**

All data collected will be included in a report to be submitted to the study grant sponsor. The data will be scanned and sent through secure electronic mail (e-mail). The report will be legible. Any errors will be corrected with a single line strike-through that does not obscure the original entry and annotated with the investigator's initials and current date. No data will be withheld from the report and any missing data will be noted with the reason for why it is missing. Frequency of case report submissions to the grant sponsor will be decided between the investigator and grant sponsor.

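### Section 6.3 ties the early termination appointment to a subject's own choice to leave, so subjects withdrawn due to an adverse event are not asked to attend the exit visit

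*Combined protocol and SAP*

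**What the plan says.** **Routes out of the study (6.2).** The section names two active routes side by side: "The subject will be discontinued from the study if the subject withdraws, is withdrawn due to an adverse event". The third is a subject who can no longer be located. For every route it adds: "Any reason for discontinuation must be documented along with information about the health of the subject at the time of withdrawal".

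**The exit visit (6.3).** The trigger is "If the subject elects to discontinue the study prior to completion, the subject will be asked to attend an early termination appointment". On content, the section says "It will include the procedures of a follow-up office visit, with the addition of a complete history and physical". The appointment stands in for the final office visit, and attendance carries increased compensation.

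**What a follow-up visit contains (5.2.2 to 5.2.4).** Vital signs, planimetry and digital assessment of the great toe, clinical assessment of the toenails, debridement, safety laboratory tests as needed, and monitoring for adverse events.

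**Other safety provisions.** Section 7.2 says "Follow-up evaluation and treatment will continue until the adverse event has resolved". Section 10.5 says "No data will be withheld from the report". Section 7.1 analyses safety on intention-to-treat and per-protocol bases and defines the first set thus: "The intention-to-treat population will include each patient receiving at least one dose of the medication, with at least one post-baseline assessment".

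**The concern.** The two active routes in 6.2 differ in who decides. In one the subject leaves; in the other the subject is taken out. Section 6.3 depends on the verb *elects*, which fits only the first. Subjects who cannot be located could not attend in any case. That leaves subjects withdrawn due to an adverse event as the contactable leavers who are not assigned the exit visit.

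The documents give no reason for treating the two groups differently, and it looks like a drafting slip. Learning about safety in a diabetic cohort is a stated goal (2.1), and the type and frequency of adverse events are endpoints (2.4.3). The stake is therefore the completeness of safety information in a small group: whether all events since the last visit are asked about in a standard way, and whether vital signs and a complete history and physical are recorded at exit.

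**Working it through.** The plan gives no figure on this point, so there is none to reproduce. The check has a textual part and a sizing part.

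**1. What each contactable leaver is assigned**

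| Item | Subject elects to leave | Subject withdrawn due to an adverse event |
|---|---|---|
| Reason and health information documented (6.2) | Yes | Yes |
| Follow-up of a known adverse event to resolution (7.2) | Yes | Yes |
| Request to attend the exit visit (6.3) | Yes | Not stated |
| Vital signs and monitoring for all adverse events at exit (5.2.2, 5.2.4, through 6.3) | Yes, if attended | Not stated |
| Complete history and physical at exit (6.3) | Yes, if attended | Not stated |

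Section 6.2 does not say what the health information must contain. Section 7.2 sets no visit, examination or timing, and it concerns an event already known. Scheduled visits are 10 weeks apart (5.2), so up to 10 weeks may have passed since adverse events were last asked about in a standard way.

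**2. How many subjects this could concern**

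Inputs:
- planned number of subjects: 48 (2.2);
- discontinuation due to adverse events on efinaconazole in two phase III studies: 3.2% and 1.9% (1.4);
- efinaconazole group sizes: 653 and 574 (3.1).

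Assumption: these rates carry over to this cohort.

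Expected number = 48 × rate:
- 48 × 0.019 = 0.91
- 48 × 0.032 = 1.54

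Chance of at least one = 1 − (1 − rate)^48:
- 1 − 0.981^48 = 0.60
- 1 − 0.968^48 = 0.79

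Pooled, with the further assumption that the group sizes in 3.1 are the denominators of the rates in 1.4:
- 21/653 = 3.2% and 11/574 = 1.9%; no other whole numbers round to these rates;
- (21 + 11)/(653 + 574) = 32/1227 = 2.6%, Clopper-Pearson 95% interval 1.8% to 3.7% (0.0179 to 0.0366);
- expected number: 48 × 0.0261 = 1.25 (0.86 to 1.76);
- chance of at least one: 1 − (1 − 0.0261)^48 = 0.72 (0.58 to 0.83).

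Given those rates, these figures are ceilings for the 6.3 gap. The rates count all discontinuations due to adverse events and do not separate subjects who chose to stop, whom 6.3 already covers, from those taken out.

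**3. The safety denominator**

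The set in 7.1 needs a post-baseline assessment, a term the plan does not define. Two readings are open:
- *Scheduled visit.* Section 5.2 says "Subjects will be assessed at the screening, at baseline, and at every 10 weeks until week 50", so the first after baseline is week 10. A subject withdrawn before then would fall outside the set.
- *Any evaluation after baseline.* Section 7.1 describes safety as assessed by recording events, and 7.2.2 has events assessed for causality. On this use, evaluating an adverse event before week 10 qualifies and the subject stays in.

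The documents give no timing of withdrawals, so the first reading could concern none or all of the subjects counted in step 2.

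**The case against.** The strongest reply is that the safety data the plan needs are already secured. The endpoints are the type and frequency of adverse events (2.4.3), and 7.1 adds nature, intensity and duration. For the event that caused withdrawal, 6.2, 7.2 and 7.2.2 supply documentation, follow-up to resolution and a causality assessment, and 7.4 adds 24-hour reporting if it is serious. Much of the exit visit concerns the toenail rather than safety. An evaluation directed at the event may tell more than a general examination. Section 6.3 may also have been written for people who need encouragement to return, and subjects with an adverse event are already under follow-up.

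Most of this stands. It does not cover other events since the last visit, for which a subject withdrawn due to an adverse event has no assigned check. A plausible intention behind 6.3 also does not change its wording, which a site would follow.

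A reader might infer three stronger points, and the documents support none of them:
- *That the adverse events behind withdrawals go unrecorded.* Sections 6.2 and 7.2 require documentation and follow-up, and 10.5 requires complete reporting.
- *That these subjects drop out of the safety analysis.* This needs the narrow reading of 7.1, and the plan's own use of the word for recording and judging adverse events points the other way. The event would be reported on either reading.
- *That the primary result is affected.* Complete cure is fixed at week 50 (2.4.1), and no section says that an early termination result is counted in its place.

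The claim that a uniform examination is more informative in these subjects than in others is also not shown by the documents, and the point does not need it.

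**Conclusion.** The gap holds as a mis-scoped rule of low consequence. As worded, 6.3 does not ask subjects withdrawn due to an adverse event to attend the exit visit. The loss is a uniform exit check, including for adverse events other than the one that led to withdrawal. The week 50 endpoint is untouched.

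The expected number is at most about one or two of 48, and it could be zero if every such subject chose to leave. This rests on phase III rates carrying over to a single-centre diabetic cohort, and the pooled figure also on the assumed denominators. These are expectations, so the number actually observed could be higher or lower. The denominator risk under 7.1 is conditional and cannot be sized. It is worth removing only because doing so is cheap. Overall this is an inexpensive improvement to consider.

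**What to change.** **Main change, 6.3.** Replace the opening condition of the section with: *If the subject is discontinued prior to completion for any reason in 6.2 and can be contacted*. The request to attend then follows as it stands.

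**Optional, 7.1.** State that safety is analysed *in all subjects receiving at least one dose, with the per-protocol set as supportive*. An early withdrawal due to an adverse event then cannot leave the denominator, whichever way the post-baseline requirement is read. The intention-to-treat definition and the target of 48 stay as they are.

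**Cost.** One or two wording changes in a single amendment, and about one or two extra uses of an existing appointment at the increased compensation 6.3 already provides. Subjects would still only be asked to attend, so some may decline and the check will not be complete.

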## **7 SAFETY ASSESSMENTS**

A safety evaluation will be conducted at every visit.

## **7.1 Safety Evaluation**

Safety will be assessed by recording the nature, intensity, and duration of treatment related adverse events. Safety analyses will be performed on both an intention-to-treat and per-protocol analysis basis. The intention-to-treat population will include each patient receiving at least one dose of the medication, with at least one post-baseline assessment.

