| Procedural pain  | 10 (1.5%)               | 7 (3.3%)          | 6 (1.0%)                | 0 (0.0%)          |
| Sinusitis  | 30 (4.6%)               | 4 (1.9%)          | 17 (3.0%)               | 5 (2.5%)          |
| Tinea pedis  | 7 (1.1%)                | 6 (2.8%)          | 4 (0.7%)                | 6 (3.0%)          |
| Upper respiratory tract infection                                | 38 (5.8%)               | 13 (6.1%)         | 35 (6.1%)               | 11 (5.5%)         |
| Urinary tract infection  | 12 (1.8%)               | 8 (3.8%)          | 12 (2.1%)               | 2 (1.0%)          |

TEAE, Treatment-emergent adverse event.

Subjects will be advised to contact study coordinators if they notice signs of any of the aforementioned adverse effects.

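### The only defined safety set requires a post-baseline assessment, so a subject who is dosed but never assessed afterwards falls outside it

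*Combined protocol and SAP*

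**What the plan says.** Section 7.1 names two bases for the safety analyses: "Safety analyses will be performed on both an intention-to-treat and per-protocol analysis basis." It then gives the ITT set two joint conditions, a dose and a later assessment: "The intention-to-treat population will include each patient receiving at least one dose of the medication, with at least one post-baseline assessment." No section defines the per-protocol set, and none sets up a population of all dosed subjects.

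Section 5.2 schedules the first assessment after baseline at week 10. Until then subjects apply the solution themselves (Section 5.3).

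Events can come to light between visits. Section 3.1 says: "Subjects will be advised to contact study coordinators if they notice signs of any of the aforementioned adverse effects." Section 6.2 says of subjects who leave: "Any reason for discontinuation must be documented along with information about the health of the subject at the time of withdrawal." For those who cannot be located, it says: "After 3 documented attempts of contact, the subject will be considered discontinued."

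Two provisions bring some early leavers back to be seen. Under Section 6.3, if a subject elects to stop, "the subject will be asked to attend an early termination appointment", and under Section 7.2, "Follow-up evaluation and treatment will continue until the adverse event has resolved."

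**The concern.** A safety set normally needs exposure and nothing more. Here it also needs a later assessment, so membership depends on what happened after the drug was applied. A subject who stops early and does not return is exposed but not counted.

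This matters because the study has no control arm (Section 2.1) and its safety endpoints are the type and frequency of adverse events (Section 2.4.3). The absolute figures are the safety result, and no comparator is subject to the same rule. Leaving out dosed subjects can lower the count of subjects with an event but cannot raise it. The rate can move in either direction, because the denominator shrinks as well.

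**Working it through.** **Step 1: who is in which set.** Consider subjects who have applied at least one dose.

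| Subject | Later assessment? | In ITT under Section 7.1? |
|---|---|---|
| Attends week 10 or any later visit | Yes | Yes |
| Stops early, attends the early termination appointment (6.3) | Yes | Yes |
| Has an adverse event and is evaluated in follow-up (7.2) | Yes | Yes |
| Lost, with nothing further known | No | No |
| Never seen again, but an event is known from a call (3.1) or the withdrawal record (6.2) | Depends on the meaning of assessment | No if a visit is required; arguably yes otherwise |

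The fourth row follows directly from the text. The fifth depends on a term that no section defines. Section 5.2 and the opening of Section 7 link assessments and safety evaluations to visits, which favours exclusion. Section 7.1 describes safety as assessed by recording events, and Section 7.2.2 has events assessed for causality, which leaves a wider reading open. The per-protocol set is undefined and cannot be relied on to bring either subject back in.

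**Step 2: inputs for the size.** The plan gives no expected adverse event rate for this study and no number of subjects dosed but never assessed, so it has no figure of its own to reproduce. The inputs are:

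- n = 48 ITT subjects (Sections 2.2 and 2.3).
- An uncommon event for illustration: application site dermatitis, 23/653 = 3.5% on active treatment in the first phase III study (Section 3.1). Then 48 x 0.035 = 1.68, taken as e = 2 subjects.
- k = 1 or 2 dosed subjects never assessed. This is an assumption. For scale only, discontinuation for adverse events in the two phase III studies was 1.9% and 3.2% (Section 1.4), or 48 x 0.019 = 0.9 to 48 x 0.032 = 1.5 subjects. How many of these would leave before any assessment is not given, and the figures do not cover losses for other reasons.

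**Step 3: formula.** The ITT rate is e/n. The all-dosed rate is (e + j)/(n + k), where j of the k unassessed subjects have a known event and j lies between 0 and k. The all-dosed rate is below the ITT rate when j/k is less than e/n, and above it when j/k is greater.

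**Step 4: results.** The ITT rate is 2/48 = 4.2%.

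| k | No known event among them (j = 0) | Known event in all of them (j = k) |
|---|---|---|
| 1 | 2/49 = 4.1% | 3/49 = 6.1% |
| 2 | 2/50 = 4.0% | 4/50 = 8.0% |

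Silent losses therefore make the ITT rate too high by 0.1 to 0.2 percentage points. Unassessed subjects who all have a known event make it too low by 2.0 points (k = 1) or 3.8 points (k = 2).

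The exact 95% interval for 2/48 is 0.5% to 14.3%, which is wider than any of these shifts.

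**The case against.** The best defence is that little is lost. The early termination appointment and the follow-up of adverse events bring many early leavers to an assessment. Section 7.4 requires events to be documented and serious ones reported within 24 hours, and Section 10.5 requires all collected data to go into the report with reasons for anything missing. The clearest case, the silent loss, removes no known event and shifts the rate by a fraction of a point. The larger shifts need an unassessed subject with a known event, and whether that subject is excluded depends on an undefined term. The 8.0% needs both assumed subjects to have the same event without either being evaluated, and it starts from 1.68 rounded up to 2.

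Most of this stands, and it is why the point is minor. It does not close the gap. The appointment is only requested, and it does not reach subjects who cannot be located. Sections 7.4 and 10.5 govern recording and reporting, and neither places a subject in a numerator or a denominator.

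A reader might go further in four ways that the documents do not support:

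- *Adverse events are hidden.* They are not. They remain recorded and reported, and only the analysed rate is affected.
- *The adverse event rate is bound to be understated.* It is not. Silent losses push it the other way.
- *The target of 48 ITT subjects conflicts with the 96 to be screened.* No contradiction is shown. Section 2.3 allows enrolment to be extended to reach 48, and the 96 in Section 4 is an anticipated number resting on a screen rate that is not further defined.
- *The cure rates are inflated by the same rule.* Section 7.1 is a safety section. No section makes its ITT set the denominator for cure or says how missing week-50 outcomes are counted.

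**Conclusion.** The point holds and is minor. As written, a dosed subject lost without any later assessment is outside the only safety set that the protocol defines. That part needs no assumption. The extension to a subject whose event is known by other contact is conditional: it holds if an assessment means a visit, which is the more natural reading of Section 5.2 and the opening of Section 7 but is not stated.

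The size cannot be known from the documents. With one or two such subjects assumed, an uncommon event analysed as 4.2% would lie between 4.0% and 8.0% among all dosed subjects. The upper end requires every unassessed subject to have a known event. The direction of the error is not fixed.

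**What to change.** In Section 7.1:

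- Make the primary safety set every subject who applied at least one dose, with no assessment requirement, and count adverse events reported by any contact.
- Keep the ITT and per-protocol safety analyses as supportive. Define the per-protocol set, and say whether a post-baseline assessment means a visit or includes other documented contact.
- Report the number of subjects dosed but never assessed after baseline, with any events known for them.

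The cost is a few lines of wording and one more denominator in the safety tables. The reported rate may move slightly in either direction.
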